2.1.7 Rationale for a Large Multicenter Trial of Preoxygenation

Because of the imperative to optimize emergency tracheal intubation in clinical care, the common use of both preoxygenation with non-invasive positive pressure ventilation and preoxygenation with facemask oxygen in current clinical practice, and the lack of existing data from randomized trials to definitively inform whether preoxygenation strategy effects the rate of hypoxemia, examining the approach to preoxygenation during emergency tracheal intubation represents an urgent research priority. To address this knowledge gap, we propose to conduct a large, multicenter, randomized clinical trial comparing preoxygenation with non-invasive positive pressure ventilation versus preoxygenation with facemask oxygen with regard to hypoxicemic during tracheal intubation of critically ill adults in the ED or ICU.

2.2. Primary Aim and Hypothesis

2.2.1 Study Aim:

To compare the effect of preoxygenation with non-invasive positive pressure ventilation versus preoxygenation with facemask oxygen on hypoxemia during tracheal intubation of critically ill adults.

2.2.2 Study Hypothesis:

Among critically ill adults undergoing tracheal intubation, preoxygenation with non-invasive positive pressure ventilation will reduce the incidence of hypoxemia between induction to 2 minutes after tracheal intubation, compared to preoxygenation with facemask oxygen.

2.3 Study Description

We will conduct an investigator-initiated, non-blinded, pragmatic, parallel-group, randomized trial evaluating the effect of preoxygenation with non-invasive ventilation versus preoxygenation with a facemask on the incidence of hypoxemia among critically ill adults undergoing tracheal intubation in the ED and ICU.

3. STUDY POPULATION AND ENROLLMENT

3.1 Inclusion Criteria:

1. Patient is located in a participating unit
2. Planned procedure is tracheal intubation using a laryngoscope and sedation
3. Planned operator is a clinician expected to routinely perform tracheal intubation in the participating unit.

3.2 Exclusion Criteria:

1. Patient is receiving positive pressure ventilation by a mechanical ventilator, bag-mask device, or laryngeal mask airway
2. Patient is known to be less than 18 years old
3. Patient is known to be pregnant
4. Patient is known to be a prisoner
5. Immediate need for tracheal intubation precludes safe performance of study procedures
6. Patient is apneic, hypopneic, or has another condition requiring positive pressure ventilation between enrollment and induction
7. Operator has determined that preoxygenation with non-invasive positive pressure ventilation or preoxygenation with a facemask is required or contraindicated for optimal care of the patient

4. CONSENT

Non-invasive positive pressure ventilation and facemask oxygen are both common approaches to preoxygenation during emergency tracheal intubation in the ED and ICU. Both represent standard of care treatments in current clinical practice.(8, 22) Results from prior clinical trials are conflicting and do not demonstrate superiority of one approach over the other. Consequently, some guidelines recommend non-invasive positive pressure ventilation and other guidelines recommend facemask oxygen.(23-26) As a result, significant variation exists in the approach to

preoxygenation in current clinical practice, with both non-invasive positive pressure ventilation and facemask oxygen used commonly.(8, 27, 28). This trial will enroll patients who are undergoing emergency tracheal intubation as part of their clinical care for whom treating clinicians have determined that preoxygenation with EITHER non-invasive positive pressure ventilation OR facemask oxygen would be consistent with the optimal care of the patient.

We will request a waiver of informed consent because the study involves minimal incremental risk and obtaining informed consent would be impracticable.

Participation in this study involves minimal incremental risk because:

- All patients eligible for the study are already undergoing tracheal intubation with preoxygenation as part of their clinical care
- Preoxygenation with non-invasive positive pressure ventilation and preoxygenation with facemask oxygen are both standard-of-care interventions that are commonly used in current clinical care
- No benefits or risks are currently known to differ between the two approaches
- Both approaches have determined to be acceptable options for the optimal care of the patient by treating clinicians (otherwise the patient is excluded from the study)

Obtaining informed consent would be impracticable because:

- **The expected medical condition of patients requiring emergency tracheal intubation in the ED or ICU is critical.** Based on prior trials in the same patient population and setting, approximately 70% of patients eligible for the PREOXI trial will be experiencing encephalopathy (altered mental status) due to their critical illness. The anticipated median Glasgow coma scale score is 11 (equivalent to moderate brain injury). Among the minority of patients whose level of consciousness is not impaired, 45-55% will be experiencing acute delirium. Thus, most patients eligible for PREOXI will not have the capacity to provide informed consent. Further, family members or legally authorized representatives (LAR) are frequently unavailable when critically ill patients undergo intubation in the ED or ICU.
- **The time available for patients or LARs to consider participation will be insufficient.** Even when a patient retains capacity or a LAR is immediately available, a meaningful informed consent process is precluded by the rapid clinical events leading up to emergency tracheal intubation. No published literature has quantified the time from clinicians' decision to perform emergency tracheal intubation (the inclusion criteria for PREOXI) until the initiation of the intubation procedure (completion of the PREOXI intervention). In a convenience sample of 25 consecutive intubations in the VUMC ED or ICU, approximately 50% of intubations occurred within 5 minutes after treating clinicians verbalized the decision to intubate or ordered an induction medication.

Obtaining informed consent for research requires study personnel to assess decisional capacity, identify a LAR when appropriate, review the informed consent document in a quiet setting, and provide sufficient time for the patient or LAR to process the information, assess the risks and benefits of participation, and ask questions. Meaningful informed consent cannot be executed in the 5 minutes between the decision to perform emergency tracheal intubation and initiation of the procedure. Emergency tracheal intubation of critically ill adults is a time-sensitive procedure for which every minute of

delay increases the likelihood of hypoxemia, hypotension, and peri-procedural cardiac arrest. Delaying emergency tracheal intubation for a critically ill adult to attempt a meaningful informed consent process would be unsafe, impracticable, and unethical.

Because the study involves minimal incremental risk, the study would not adversely affect the welfare or privacy rights of the participant, and obtaining informed consent would be impracticable, we will request a waiver of informed consent. Numerous previous randomized trials comparing two standards of care for emergency intubation have been completed under a waiver of informed consent [NCT 0040102, NCT 03928925, NCT 02497729, NCT 02051816, NCT 00441792].(7, 29-32)

4.1 Provision of Information after Participation

Information regarding the study will be made available to each patient and family following intubation using a patient and family information sheet. The sheet will inform the patient of his or her enrollment in the PREOXI study, describe the study, and provide contact information for the research team for any questions or concerns.

5. ENROLLMENT AND RANDOMIZATION

5.1 Study Enrollment Locations:

- Participating emergency departments
- Participating intensive care units

5.2 Study Sites:

- **Vanderbilt University Medical Center**
- **Other locations**

5.3 Enrollment and Randomization

All patients requiring emergency tracheal intubation in a participating ED or ICU will be screened for eligibility for the PREOXI trial using the eligibility criteria in Section 3. Patients who do not meet inclusion criteria will be considered ‘ineligible’. Patients who meet inclusion criteria but also meet at least one exclusion criterion will be considered ‘excluded.’ For patients who are excluded, the reason for exclusion will be recorded. For patients who do meet eligibility criteria but are not enrolled, the reason will be recorded.

At enrollment, patients will be randomized in a 1:1 ratio to preoxygenation with non-invasive positive pressure ventilation or preoxygenation with facemask oxygen using randomly permuted blocks of variable size. The randomization will be stratified by study site (i.e., each participating ED or ICU will comprise a different stratum). The study group assignment will be placed in opaque randomization envelopes, which will be located within participating units. Study group assignment will remain concealed to study personnel and treating clinicians until after the decision has been made to enroll the patient in the study.

To facilitate rapid enrollment during this time-sensitive procedure, sequentially numbered randomization envelopes will be located adjacent to the equipment required for emergency

tracheal intubation (i.e., airway equipment cart, ICU work room). When the need for emergency tracheal intubation is recognized, envelopes will be obtained by the treating clinician performing the intubation (referred to as the “operator”) or by a delegate while the operator sets up the equipment required for intubation. Inclusion and exclusion criteria will be posted with randomization envelopes and printed on the outside of enrollment envelopes. As the operator sets up the equipment for emergency tracheal intubation, a verbal “pre-procedural time-out” (described below) will be performed. Based on the experience from our 8 prior randomized clinical trials using the same process to perform randomization and group assignment during emergency tracheal intubation, all enrollment procedures can be completed in less than one minute. For a small number of particularly urgent intubations (e.g., an intubation for cardiac arrest), the urgency of the procedure or the limited availability of clinical personnel will preclude obtaining and opening the randomization envelope. These cases will be excluded using the exclusion criterion that states “Immediate need for tracheal intubation precludes safe performance of study procedures” (see Section 3).

As with all trials conducted to date by our investigators, we will evaluate for the possibility of selection bias via the systematic exclusion of a particular groups of patients. A prospective list of excluded patients will be maintained by site PIs. Data captured on excluded patients will be limited to date of exclusion and reason for exclusion. The number of patients excluded and reasons for excluded will be reported at the time of trial publication via a consort diagram. No patient-level information on excluded patients will be entered into the study database. The coordinating center will not receive any patient-level data on excluded participants.

5.3.1 Pre-Procedural Time-Out to Prevent Enrollment of Ineligible Patients

The enrollment materials for the trial will include instructions for a pre-procedural timeout in which treating clinicians or a delegate recite aloud the inclusion and exclusion criteria and confirm eligibility prior to enrollment. This process requires less than 10 seconds and can be easily completed while the equipment and medications needed for tracheal intubation are being obtained. This approach has been successfully used to confirm eligibility prior to enrollment in multiple prior trials [NCT03928925, NCT03787732]. (33)

5.3.2 Monitoring and Reporting of Eligibility of Enrolled Patients

For all enrolled patients, study personnel will independently verify eligibility criteria at the time of study record creation. In the instance that a patient is enrolled who did not meet eligibility criteria, this will represent a protocol violation. Site investigators will report such a protocol violation to the trial primary investigators and coordinating center **within 24 hours** of becoming aware of the occurrence of a protocol violation. The primary investigators and coordinating center will report the details of such a protocol violation to the IRB **within 7 days** of becoming aware of the occurrence of a protocol violation.

5.3.3 Handling of Patients Found to Be Prisoners after Enrollment

Prisoners typically present with obvious physical signs such as prison uniforms, handcuffs, and the presence of law enforcement. Training of treating clinicians and the enrollment procedures listed above (posting of inclusion and exclusion criteria alongside enrollment envelopes and a “pre-enrollment time-out” with verbal recitation of eligibility criteria) have proven to be effective in preventing the enrollment of prisoners in recent trials.

If a patient who presents to the ED or ICU is not known to be a prisoner at the time of enrollment and following enrollment is discovered to be a prisoner or becomes a prisoner between enrollment and the end of study follow up, all study procedures will stop immediately, the patient will be withdrawn from the study, and the patient's study record will be expunged of all study data. Because both study interventions are one-time, standard-of-care interventions which the patient was likely to receive in clinical care even if not participating in research, no further follow-up will occur.

6. BLINDING

Given the nature of the trial intervention, blinding of patients and treating clinicians to study group assignment is not possible.

7. STUDY INTERVENTIONS

7.1 Treatment of Study Patients

For enrolled patients, study group assignment determines only the approach to preoxygenation. All other aspects of the intubation procedure will be at the discretion of the operator, including patient positioning, choice of sedative agent, use of a neuromuscular blocker, choice of laryngoscope, laryngoscope blade size, use of a bougie to intubate the trachea, use of external laryngeal manipulation to optimize laryngeal view, and endotracheal tube diameter.

The administration of additional supplemental oxygen by nasal cannula is not controlled by the study and is permitted in both groups in any phase of the tracheal intubation procedure, including during laryngoscopy (referred to as “apneic oxygenation”). The administration of ventilation via a bag-mask device will be permitted in both groups between induction and laryngoscopy.

Operators may use a non-assigned approach to preoxygenation at any time if it is felt to be required for the safe management of the patient. Use of a non-assigned preoxygenation strategy as the initial approach to preoxygenation will be collected and considered to represent a “crossover.” For all patients in the trial, best practices in emergency tracheal intubation will be encouraged according to clinical protocols in the study settings.

7.2 Preoxygenation with Non-Invasive Positive Pressure Ventilation Group

Patients assigned to preoxygenation with non-invasive positive pressure ventilation will receive non-invasive mechanical ventilation via a tight-fitting mask from the initiation of preoxygenation until the initiation of laryngoscopy. Trial protocol will not dictate the brand or type of mechanical ventilator that will be used to deliver non-invasive ventilation.

7.3 Preoxygenation with Facemask Oxygen Group

For patients randomized to preoxygenation with facemask oxygen, supplemental oxygen will be administered via a non-rebreather mask or bag-mask device without manual ventilation from the initiation of preoxygenation until induction. Trial protocol will not dictate the brand or type of facemask. The decision between use of a non-rebreather mask and use of a bag-mask device will be made by treating clinicians. The decision of whether to provide manual ventilation with a bag-mask device between induction and laryngoscopy will be made by treating clinicians.

8. RECORDED STUDY OUTCOMES

8.1 Primary Outcomes

- Hypoxemia, defined as a peripheral oxygen saturation < 85% during the interval between induction and 2 minutes after tracheal intubation

8.2 Secondary Outcomes

- Lowest oxygen saturation during the interval between induction and 2 minutes after tracheal intubation

8.3 Safety Outcomes

- Operator-reported aspiration
- Fraction of inspired oxygen at 24 hours after induction
- Oxygen saturation at 24 hours after induction
- New pneumothorax, defined as radiology report of new pneumothorax on chest imaging in the 24 hours after induction.
- New infiltrate, defined as radiology report of new infiltrate on chest imaging in the 24 hours after intubation.

8.4 Exploratory Outcomes

- Procedural Characteristics & Complications
 - Severe hypoxemia (lowest oxygen saturation of <80%) between induction and two minutes after tracheal intubation
 - Very severe hypoxemia (lowest oxygen saturation of <70%) between induction and two minutes after tracheal intubation
 - Oxygen saturation at induction
 - Systolic blood pressure at induction
 - Duration from induction to successful intubation (duration of the intubation procedure)
 - Cormack-Lehane grade of glottic view on first attempt
 - Successful intubation on the first attempt
 - Number of laryngoscopy attempts
 - Number of attempts at passing a bougie
 - Number of attempts at passing an endotracheal tube
 - Cardiovascular collapse, defined as a composite of one or more of the following between induction and 2 minutes after intubation:
 1. Systolic blood pressure < 65 mmHg
 2. New or increased vasopressor
 3. Cardiac arrest not resulting in death within 1 hour of induction
 4. Cardiac arrest resulting in death within 1 hour of induction
- Clinical Outcomes
 - 28-day in-hospital mortality
 - Ventilator-free days to 28 days
 - ICU-free days to 28 days

9. DATA COLLECTION

Data collected for the purposes of this study will come from three sources: [1] variables documented in the electronic health record as part of clinical care, [2] variables recorded by clinical staff's bedside observation during the intubation procedure, and [3] variables reported by the operator immediately following the intubation procedure. Data from the electronic medical record will be collected by trained study personnel (key study personnel) using a standardized electronic case report form. It is infeasible to have research staff present during each emergency tracheal intubation. Therefore, clinical staff not participating in the tracheal intubation procedure will collect data elements relevant to outcomes of emergency tracheal intubation using a standardized electronic case report form. These variables are readily available by bedside observation and do not require interaction with the patient but are not uniformly documented in the electronic health record (e.g., lowest oxygen saturation and lowest blood pressure from induction to two minutes after tracheal intubation). Immediately following the intubation procedure, the operators will record data elements known only to them (e.g., glottic view obtained during the procedure and visualization of gastric aspiration in the oropharynx). Operators and clinical staff observing the procedure at the bedside will not be considered key study personnel. Training will be provided to clinicians who may serve as operators or bedside observers. The activities of these clinicians will be limited to the reporting of data routinely reported as part of clinical care.

The following variables will be recorded:

Baseline:

- age
- sex
- race and ethnicity
- height
- weight
- body mass index
- Acute Physiology and Chronic Health Evaluation (APACHE II) score
- active medical problems at the time of enrollment
- comorbidities
- indication for intubation
- vasopressor receipt in the hour prior to enrollment
- highest FiO₂ in the hour prior to enrollment
- lowest SpO₂/FIO₂ ratio (or PaO₂/FIO₂ ratio) in the hour prior to enrollment
- Glasgow Coma Scale score
- oxygen delivery device at enrollment
- assessment of the likelihood of a difficult intubation
- presence of difficult airway characteristics
 - limited mouth opening
 - limited anatomic neck mobility
 - cervical immobilization due to trauma
 - increased neck circumference
 - facial trauma
 - obesity

- body fluids anticipated to obscure laryngeal view
- operator's level of training and specialty
- operator's prior intubation experience

Peri-procedural:

Enrollment to induction

- SpO₂ and FiO₂ at enrollment
- oxygen saturation from enrollment to induction
- approach to preoxygenation
- duration of preoxygenation

Induction to first laryngoscopy attempt

- time of sedative administration (induction)
- sedative agent and dose
- neuromuscular blocking agent and dose
- administration of an intravenous fluid bolus prior to induction
- administration of a vasopressor prior to induction
- SpO₂ at induction
- systolic blood pressure at induction
- approach to oxygen administration and ventilation between induction and laryngoscopy

First laryngoscopy attempt to successful intubation

- time of start of first laryngoscopy attempt
- laryngoscope model, blade size, blade shape on first attempt
- use of video screen (if applicable) on first laryngoscopy attempt
- best Cormack-Lehane grade of glottic view on the first laryngoscopy attempt
- presences of body fluids obstructing laryngeal view
- presence of upper airway obstruction or edema
- receipt of chest compressions at time of first laryngoscopy attempt
- number of intubation attempts
 - number of times laryngoscope entered mouth
 - number of times bougie entered mouth (if applicable)
 - number of times endotracheal tube entered mouth
- reason for failure of first intubation attempt (if applicable)
- device(s) used on subsequent intubation attempts (if applicable)
- necessity of an additional operator
- esophageal intubation
- injury to the teeth
- operator-reported aspiration between induction and intubation
- time of successful tracheal intubation
- endotracheal tube size
- lowest SpO₂ from induction until 2 minutes after intubation
- lowest systolic blood pressure from induction until 2 minutes after intubation
- new or increased vasopressor use from induction until 2 minutes after intubation
- cardiac arrest from induction until 2 minutes after intubation not resulting in death within 1 hour of induction

- cardiac arrest from induction until 2 minutes after intubation resulting in death within 1 hour of induction

In-hospital:

24 hours after enrollment

- new pneumothorax detected in the first 24 hours after enrollment
- vasopressor receipt at 24 hours after enrollment
- SpO₂ at 24 hours after enrollment
- FiO₂ at 24 hours after enrollment
- PEEP at 24 hours after enrollment
- systolic blood pressure at 24 hours after enrollment

28 days after enrollment

- 28-day in-hospital mortality
- ventilator-free days
- ICU-free days

10. Risks and Benefits

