10.1 Risks of Tracheal Intubation in the ED or ICU

Patients who are severely ill enough to require emergency tracheal intubation in the ED or ICU as part of their clinical care are at high risk of complications. Many patients are undergoing intubation for hypoxemia or hemodynamic instability. Severe hypoxemia or cardiovascular instability occurs during nearly half of intubations in the ED and ICU (1, 2, 4, 5). Hypoxemia and hypotension during intubation are associated with an increased risk of cardiac arrest and death.(9, 10) Cardiac arrest occurs in 1-in-25 cases of emergency tracheal intubation.

Other complications during intubation may include aspiration (approximately 2.8% of cases), esophageal intubation (1.3%) injury to oral or dental structures (0.2%), and pneumothorax (0.1%). The long-term consequences of complications occurring during emergency tracheal intubation are unclear. Neurologic recovery from traumatic brain injury may be worse after hypoxemia due to secondary ischemic insult.(11)

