Copyright © 2023 The Authors. Published by Elsevier Inc under license from the American College of Chest Physicians. This is an open access article under the CC BY-NC-ND license (<http://creativecommons.org/licenses/by-nc-nd/4.0/>).

DOI: <https://doi.org/10.1016/j.chstcc.2023.100014>

ventilation may reduce air entrainment by delivering a higher inspiratory flow rate of oxygen and by minimizing leaks. Additionally, noninvasive ventilation increases the mean airway pressure and recruits atelectatic lung, potentially reducing shunting. Compared with an oxygen mask, noninvasive ventilation may take longer to initiate and potentially may increase the risk of gastric insufflation and aspiration.

Two small randomized trials have compared these two approaches to preoxygenation. The first trial found that, among 53 patients in the ICU undergoing tracheal intubation in two hospitals, noninvasive ventilation increased the lowest oxygen saturation compared with the effects of an oxygen mask (mean lowest oxygen saturation, 93% vs 81%, respectively; $P < .001$) with no difference between groups in the incidence of aspiration

(6% vs 8%).¹¹ Among 201 patients in the ICUs of six hospitals, the second trial found no difference in the severity of illness in the 7 days after intubation and an incidence of hypoxemia during intubation of 18.4% in the noninvasive ventilation group vs 27.7% in the oxygen mask group ($P = .10$).¹² Thus, whether noninvasive ventilation for preoxygenation in critically ill adults undergoing emergency tracheal intubation decreases the incidence of hypoxemia compared with an oxygen mask remains unknown. We designed the Pragmatic Trial Examining Oxygenation Prior to Intubation (PREOXI) to test the hypothesis that, among critically ill adults undergoing emergency tracheal intubation in the ED and ICU, preoxygenation with noninvasive ventilation decreases the incidence of hypoxemia compared with preoxygenation with an oxygen mask.

Study Design and Methods

This article was written in accordance with Standard Protocol Items: Recommendations for Interventional Trials guidelines (Table 1, e-Appendix 1).¹³

Study Design

PREOXI is a pragmatic, multicenter, nonmasked, parallel-group randomized trial comparing preoxygenation using noninvasive ventilation with preoxygenation using an oxygen mask among critically ill adults undergoing emergency tracheal intubation in

TABLE 1] Schedule of Enrollment, Interventions, and Assessments in PREOXI

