of baseline, periprocedural, and in-hospital variables are provided in [e-Table 1](#).

Primary Outcome

The primary outcome is the incidence of hypoxemia, defined as a peripheral oxygen saturation of < 85% during the interval between induction and 2 min after intubation.

Secondary Outcome

The sole secondary outcome is the lowest oxygen saturation during the interval between induction and 2 min after tracheal intubation.

Additional Outcomes

[Table 3](#) reports the safety outcomes, exploratory procedural outcomes, and exploratory clinical outcomes.

TABLE 3] Study Outcomes

Outcome Type	Description
Primary	Incidence of hypoxemia, defined as a peripheral oxygen saturation of < 85% during the interval between induction and 2 min after tracheal intubation.
Secondary	Lowest oxygen saturation during the interval between induction and 2 min after tracheal intubation.
Safety	Incidence of operator-reported aspiration. FiO_2 at 24 h after induction.
	Oxygen saturation at 24 h after induction.
	Incidence of pneumothorax, defined as radiology report of new pneumothorax on chest imaging in the 24 h after induction. If no chest imaging is available before induction, any pneumothorax in the 24 h after induction will be assumed to be new.
	New infiltrate, defined as radiology report of new infiltrate on chest imaging in the 24 h after intubation. If no chest imaging is available before induction, any infiltrate in the 24 h after induction will be assumed to be new.
Exploratory procedural	Incidence of severe hypoxemia, defined as the lowest oxygen saturation of < 80% between induction and 2 min after tracheal intubation.
	Incidence of very severe hypoxemia, defined as the lowest oxygen saturation of < 70% between induction and 2 min after tracheal intubation.
	Oxygen saturation at induction.
	Systolic BP at induction.
	Duration from induction to successful intubation (duration of the intubation procedure).
	Cormack-Lehane grade of glottic view on first attempt.
	Successful intubation on the first attempt
	No. of laryngoscopy attempts.
	No. of attempts at passing a bougie.
	No. of attempts at passing an endotracheal tube.
	Incidence of cardiovascular collapse, defined as a composite of ≥ 1 of the following between induction and 2 min after intubation: systolic BP < 65 mm Hg, new or increased vasopressor administration, cardiac arrest not resulting in death within 1 h of induction, cardiac arrest resulting in death within 1 h of induction.

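### The aspiration item opens at induction, after most of the noninvasive ventilation time has passed, while the safety outcome it feeds has no stated window

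*Combined protocol and SAP*

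**What the plan says.** Section 9 of the protocol, in the block on the first laryngoscopy attempt, lists "operator-reported aspiration between induction and intubation". Versions 1.0 and 1.1 word it identically. The outcome itself appears in Section 8.3 as "Operator-reported aspiration" and in Table 3 of the published SAP as "Incidence of operator-reported aspiration". Neither gives a window, although the other four safety outcomes in Section 8.3 of v1.1 each carry a 24-hour time point or period.

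Section 7.2 assigns the NIV arm to "non-invasive mechanical ventilation via a tight-fitting mask from the initiation of preoxygenation until the initiation of laryngoscopy". Figure 1 of the published SAP divides that period: NIV is mandated until induction and recommended from induction to laryngoscopy. In the mask arm, Figure 1 mandates oxygen without ventilation until induction. After that the arms may converge, since Section 7.1 states: "The administration of ventilation via a bag-mask device will be permitted in both groups between induction and laryngoscopy".

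The introduction to the published SAP says that "noninvasive ventilation may take longer to initiate and potentially may increase the risk of gastric insufflation and aspiration".

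**The concern.** The item covers the phase that the trial leaves largely to the operator and omits the phase that it randomises. Patients already receiving positive pressure ventilation are excluded, so NIV before induction is exposure created by the allocation. The Discussion of the published SAP itself says that preoxygenation, rather than management after induction, is the trial's focus.

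Section 4 expects "approximately 70% of patients eligible for the PREOXI trial will be experiencing encephalopathy (altered mental status"). Regurgitation under a tight mask before any sedative is therefore a plausible event, although the documents give no rate for it. Read literally, the item would not count it.

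At stake is the interpretation of a safety outcome that the documents link to a potential harm of one arm. If aspiration during preoxygenation is not counted, similar recorded rates cannot show that preoxygenation with NIV is free of this risk.

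**Working it through.** The plan states no figure for the aspiration window, so there is none to reproduce. The 1,264 patients in Section 11.1 concern the primary outcome. That figure reproduces exactly (632 per group, with continuity correction), and this point does not affect it.

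**Inputs**
- Preoxygenation, T1 = 180–300 s (published SAP, Figure 1).
- Induction to laryngoscopy, T2 = 45–90 s (Figure 1).
- Laryngoscopy to intubation, T3 = 45–90 s (Figure 1).
- Background rate: "aspiration (approximately 2.8% of cases") (Section 10.1).
- 650 patients per arm (Section 11.1).

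**Step 1: share of NIV time before the window opens, T1/(T1+T2)**
- Lowest: 180/(180+90) = 67%.
- Mid-range: 240/(240+67.5) = 78%.
- Highest: 300/(300+45) = 87%.

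The item therefore covers about 13–33% of NIV time. Measured against the whole span to intubation, T1/(T1+T2+T3), the time before induction is 180/360 = 50% to 300/390 = 77%. That is a share of procedure time, because NIV ends at laryngoscopy.

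**Step 2: effect on the comparison**

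Let p1 and p0 be the aspiration risks over the whole period in the NIV and mask arms, and f1 and f0 the shares of those events before induction.

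Recorded difference = p1(1−f1) − p0(1−f0) = (p1−p0) − (p1f1 − p0f0).

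The recorded difference is below the true one only if p1f1 > p0f0, that is, if aspiration before induction is commoner with NIV. The documents give neither f1 nor f0.

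**Step 3: range, by assumption**

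Assume p0 = 2.8% and a true doubling to p1 = 5.6%, a difference of 2.8 points. Let f be either the share lost equally from both arms, or the share lost from the NIV excess alone. The recorded difference is 2.8(1−f) in both cases. The risk ratio stays 2.0 in the first case and is 1+(1−f) in the second.

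| f | Recorded difference (points) | Risk ratio, equal loss | Risk ratio, only excess lost |
|---|---|---|---|
| 0 | 2.8 | 2.0 | 2.0 |
| 10% | 2.5 | 2.0 | 1.9 |
| 50% | 1.4 | 2.0 | 1.5 |
| 87% | 0.4 | 2.0 | 1.1 |

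Power at 650 per arm is about 71% with full capture. At f = 50% it is 42% with equal loss and 28% if only the excess is lost. If the true risks are equal and f is the same in both arms, no difference is hidden.

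**Step 4: scale**

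Expected events: 0.028 × 650 = 18.2 per arm. The 95% CI half-width for the difference is 1.96 × √(2 × 0.028 × 0.972/650) = 1.8 points.

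**The case against.** A reader might infer that the plan understates aspiration with NIV, or biases the comparison toward no difference. The documents do not support that. The 67–87% is a share of time, not of aspirations. The same window applies to both arms. Gas forced into the stomach before induction may cause regurgitation after it. Section 9 describes operators recording gastric material seen in the throat, so earlier regurgitation may still be seen at laryngoscopy and counted. The window also contains a risk period: the published SAP's Discussion raises aspiration in connection with bag-mask ventilation after induction. All of this stands, and it is why attenuation is possible but not shown.

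A reader might also take aspiration to be the one harm that the documents attribute to NIV. That goes too far. Protocol Section 2.1.5 calls the concern hypothetical, the SAP calls it potential, Section 10.2 says no risks are known to differ, and Section 14.4 uses an NIV-related pneumothorax as its example.

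Other measures do reach beyond the window. New infiltrate within 24 hours is read by a radiologist unaware of assignment, and SpO2 and FiO2 are taken at 24 hours. Adverse event monitoring starts at randomization (Section 14.2). These backstops are partial. The infiltrate definition includes pulmonary edema and pneumonia, and treats any finding as new when there is no earlier imaging. Section 14.4 exempts aspiration from adverse event reporting unless someone believes it definitely, probably or possibly related. That leaves out the uncertain category that Section 14.3 otherwise includes, and the judgment is made unblinded.

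Finally, the operator form is not in the supplied text. The published SAP says only that the form records complications, with aspiration as an example. The form may not carry the Section 9 restriction.

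**Conclusion.** The point holds as a mismatch with a possible consequence. The only stated window for aspiration starts at induction, the outcome definition has none, and on nominal durations 67–87% of NIV time falls before that window. Aspiration during preoxygenation may go unrecorded in the safety outcome, and a between-arm difference may be attenuated. The direction and size of any bias cannot be determined from the documents.

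The time shares rest on Figure 1; the preprint SAP says that the duration of preoxygenation is not dictated, so actual shares will vary. The conclusion also assumes that the form follows Section 9. With about 18 expected events per arm and a half-width of 1.8 points, reassurance would be limited even with full capture. The plan emphasises estimates with confidence intervals for safety outcomes and announces no claim that aspiration is not increased. The primary outcome and sample size are untouched. This is a cheap improvement.

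**What to change.** Use one window in Section 8.3, Table 3, Section 9 and the operator form: from enrollment (envelope opening) or the initiation of preoxygenation, to intubation. Add a tick for before or after induction, and report both phases by arm. The cost is one reworded item on a form that the same operator already completes, plus matching wording in the outcome lists. A change mid-trial would leave two form versions, and the tick keeps the post-induction part comparable across them.

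The SAP revision record dates the last enrollment to October 14, 2023, so for this trial's data the usable part is the reporting. First check the form as used. If it carries the Section 9 wording, state that the outcome covers only induction to intubation, and do not conclude from it that preoxygenation itself carries no aspiration risk.
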